4.7.3.3 Clinician Global Impression of Change

The CGIC is a measure of perceived change in PV symptoms as assessed by the clinician. The clinician uses a 7-item categorical scale ranging from “very much improved” to “very much worse” to answer “How would you rate the change in the patient’s pemphigus vulgaris symptoms since the patient started taking the study drug?” ([Appendix 8](#)).

Data for CGIC will be described in the same manner as PGIC, as described in Section [4.7.3.2](#).

4.7.3.4 Remission Endpoints

Several remission endpoints will be evaluated in this study to assess the degree of remission attained within each treatment arm. The following five remission endpoints will be evaluated:

- Sustained Complete Remission
- Complete Remission – off therapy
- Complete Remission – on minimal therapy
- Partial Remission – off therapy
- Partial Remission – on minimal therapy

Complete remission (CR) off-therapy may be regarded as a subset of sustained CR; a patient who achieves CR off-therapy may also achieve sustained complete remission. The four categories of CR on/off therapy and partial remission (PR) on/off therapy will be regarded as mutually exclusive events. A patient will fall into the category that is the highest degree of remission obtained.

All remission endpoints will be derived using PDAI^a, prednisone (or equivalent), treatment failure, or withdrawal date in the same manner as that used for sustained complete remission in Section [4.7.1](#).

4.7.3.5 Complete Remission

CR is defined as absence of new or established lesions on 0 mg/day prednisone or equivalent for at least 8 consecutive weeks. Two categories of complete remission will

Rituximab—F. Hoffmann-La Roche Ltd
26/Statistical Analysis Plan WA29330

be evaluated: off-therapy and on minimal therapy. A patient will be considered a complete responder if the following criteria are achieved and maintained for a minimum of 8 consecutive weeks:

- CR off-therapy: PDAI^a=0 and prednisone=0 mg/day
- CR on minimal therapy: PDAI^a=0 and $0 < \text{prednisone} \leq 10$ mg/day

The number and percentage of patients achieving CR by Week 24 and Week 52 will be summarized descriptively. A patient is considered a responder at a visit if they have demonstrated and maintained a response by that visit.

All data handling methods will follow those used for the derivation and classification of sustained complete remission.

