3.1.2 Corticosteroid Treatment

Patients eligible for this study will be receiving 60–120 mg/day background oral prednisone or equivalent (1.0–1.5 mg/kg/day) at study entry. During the screening period (up to 28 days), the daily corticosteroid dose may be tapered, as directed by the investigator on the basis of disease activity and tolerability to reach a dosage of 60 or 80 mg/day by Day 1. Thereafter, corticosteroid treatment should then be tapered according to the treatment guideline in [Table 1](#), which provides recommended doses based on the presence of disease activity, defined as the appearance of new lesions or the extension of established lesions. The decision to taper the corticosteroid dose can be affected by physician preferences, patient tolerability, and local practices, among

Rituximab—F. Hoffmann-La Roche Ltd
32/Protocol WA29330, Version 5

other considerations. The oral corticosteroid dose may be increased during the study as needed as the primary intervention for control of disease activity. Prednisone (or equivalent) will be sourced locally.

The goal of study treatment is to maintain disease control and ultimately achieve disease remission. Oral corticosteroids will be tapered to the target prednisone (or equivalent) dosage of 0 mg/day by Week 24 (or sooner, if appropriate). From Week 24 to Week 52, the corticosteroid dosage should be maintained at 0 mg/day. However, patients who experience a disease flare (as defined in Section 3.4.1.2) at 0 mg/day should restart at Step 5 of [Table 1](#) (20 mg/day). Patients whose disease is not controlled after increasing the corticosteroid dose up to an allowable maximum dose of 240 mg/day will be considered to have experienced treatment failure and may receive standard-of-care treatment per the investigator's best medical judgment. Use of minimal concomitant topical corticosteroids will be permitted at the investigator's discretion but will be tracked carefully during the course of the study.

Table 1 Corticosteroid Treatment Guideline

Step	No. of Weeks	Daily Dose of Prednisone or Equivalent	Presence of Disease Activity ^a	
			No	Yes
1 (start) ^b	1 week	80 mg	Go to Step 2	Go to Step A
A	1 week	120 mg	Go to Step 2	Go to Step B
B	1 week	240 mg	Go to Step A	Discontinue taper ^c
2 (start) ^b	1 week	60 mg	Go 1 step forward	Go to Step 1
3	1 week	40 mg		Go 1 step back
4	2 weeks	30 mg		Go 2 steps back
5	2 weeks	20 mg		
6	2 weeks	15 mg		
7	2 weeks	12.5 mg		
8	2 weeks	10 mg		
9	2 weeks	7.5 mg		

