3.4.3 Exploratory Outcome Measures

The exploratory outcome measures for this study will include, but are not limited to, the following:

- Proportion of patients achieving a complete remission by Week 24 and by Week 52
 - Complete remission is defined as achieving wound healing with no new active lesions (i.e., PDAI activity score of 0) for at least 8 consecutive weeks during the 52-week treatment period.
- Proportion of patients achieving a partial remission by Week 24 and by Week 52
 - Partial remission is defined as the presence of transient new lesions that heal within 1 week (while the patient is receiving minimal therapy, including topical

Rituximab—F. Hoffmann-La Roche Ltd
40/Protocol WA29330, Version 5

corticosteroids). Minimal therapy is defined as ≤ 10 mg/day prednisone (or equivalent) for at least 8 consecutive weeks during the 52-week treatment period.

- Pharmacokinetics/pharmacodynamics of rituximab
 - PK/PD parameters include, but are not limited to, serum levels of rituximab, peripheral CD19+ B-cell counts, HACA, and autoantibody concentrations.
- To explore the pharmacodynamics of MMF in patients with PV
- Change in total PDAI activity score during the treatment period
- Change from baseline in anti-Dsg1 and anti-Dsg3 autoantibodies
- Change in health utilities as assessed by the EQ-5D-3L score from baseline to Week 52
- Change in HRQoL, as measured by the Skindex-29 from baseline to Week 52
- *Proportion of patients who experience treatment failure from Week 12 to Week 52*

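### SAP 4.7.3.5 analyses a narrower complete remission than protocol 3.4.3 defines, so its count can only equal or fall below the protocol's

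*SAP*

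**What the plan says.** Protocol 3.4.3, repeated in SAP 2.2.4, asks for healing with "no new active lesions (i.e., PDAI activity score of 0) for at least 8 consecutive weeks during the 52-week treatment period". Neither place attaches a prednisone dose to complete remission. Both define minimal therapy, under partial remission, as at most 10 mg/day, which includes 0.

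SAP 4.7.3.5 opens differently: "CR is defined as absence of new or established lesions on 0 mg/day prednisone or equivalent for at least 8 consecutive weeks". It then sets two categories. The first is "CR off-therapy: PDAI^a=0 and prednisone=0 mg/day". The second is complete remission on minimal therapy: PDAI activity 0 with prednisone strictly above 0 and at most 10 mg/day. Each must be "achieved and maintained for a minimum of 8 consecutive weeks". SAP 4.7.3.6 uses the same two dose bands for partial remission.

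SAP 4.7.3.4 makes the four complete and partial categories mutually exclusive and files each patient under the best one reached. On how they relate to the primary endpoint it says: "Complete remission (CR) off-therapy may be regarded as a subset of sustained CR".

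The results are tabulated by Week 24 and by Week 52 (SAP 4.7.3.5) and again by subgroup (SAP 4.7.4). Complete or partial remission at those times is a named exploratory objective (protocol 2.3).

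**The concern.** There are three separate faults.

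1. The analysis section adds a dose condition that the endpoint definition does not have, so the table would not report the protocol's endpoint.
2. The lead sentence of 4.7.3.5 allows only 0 mg/day, while its second category counts patients on up to 10 mg/day as complete responders. Two programmers could derive different headline counts from it.
3. The two bands do not join. A lesion-free patient who moves from 2.5 mg to 0 mg leaves one band and starts again from zero in the other.

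The third fault matters most at Week 24, because the protocol's taper guideline takes patients through that move a few weeks before the visit. At stake is the meaning of the Week 24 complete remission row and of the subgroup tables built on it.

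**Working it through.** **Inputs.** Protocol Table 1 (step doses and durations; start at Step 1, 80 mg, or Step 2, 60 mg). PDAI visits at Weeks 4, 8, 12, 16, 20 and 24, i.e. Days 28, 56, 84, 112, 140 and 168, each ±3 (protocol Appendix 1). PDAI of 0 is taken to hold between visits (SAP 4.7.1.2). Required run: 8 × 7 = 56 days, counted inclusively.

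**The plan's own figure.** Protocol 3.1.2 aims for 0 mg/day by Week 24 or sooner. With no step back:

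- 60 mg start: Steps 2 and 3 take 1 week each and Steps 4 to 11 take 2 weeks each, so 2 + 16 = 18 weeks. 0 mg starts on Day 127.
- 80 mg start: one week more, 19 weeks. 0 mg starts on Day 134.

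Both agree with the stated target.

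**Time in each band.** Steps 8 to 11 (10, 7.5, 5 and 2.5 mg) last 4 × 14 = 56 days: Days 71–126 from 60 mg, Days 78–133 from 80 mg. That is the required run with no day to spare.

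Days at 0 mg by Day 168: 168 − 127 + 1 = 42, or 168 − 134 + 1 = 35. Both are below 56. The off-therapy run completes on Day 127 + 55 = 182 (Week 26) or Day 134 + 55 = 189 (Week 27).

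**Result at Day 168 by first visit with PDAI 0, patient clear from then on.** Paired figures are 60 mg start / 80 mg start.

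| First clear | Days above 0 to 10 mg | Days at 0 mg | Lesion-free days, any dose | Protocol CR | SAP CR |
|---|---|---|---|---|---|
| Week 4 | 56 / 56 | 42 / 35 | 141 | yes | yes |
| Week 8 | 56 / 56 | 42 / 35 | 113 | yes | yes |
| Week 12 | 43 / 50 | 42 / 35 | 85 | yes | no |
| Week 16 | 15 / 22 | 42 / 35 | 57 | yes | no |
| Week 20 | 0 / 0 | 29 / 29 | 29 | no | no |

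For Week 12 from 60 mg: Days 84–126 are 126 − 84 + 1 = 43, Days 127–168 are 42, and 43 + 42 = 85. From 80 mg, 50 + 35 = 85.

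**Visit windows.** A Week 12 visit three days early (Day 81) gives 126 − 81 + 1 = 46 or 133 − 81 + 1 = 53 days in the upper band. A Week 24 visit on Day 171 gives 45 or 38 days at 0 mg. All stay below 56, so the Week 12 result is firm. The Week 16 result is not: a visit on Day 114 leaves 168 − 114 + 1 = 55 days, which fails the protocol definition too.

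**Faster tapers.** A patient clear throughout with 55 days at above 0 to 10 mg (Days 59–113) and 55 days at 0 mg (Days 114–168) has 110 lesion-free days at 10 mg or less and no qualifying run.

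**Direction.** Each SAP category requires PDAI 0 for 8 weeks plus a dose condition. With the same data handling, every SAP complete responder meets the protocol definition, but not the reverse.

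**Subset sentence.** Sustained complete remission (SAP 4.7.1.1) is PDAI 0 at 0 mg for 16 weeks. Off-therapy complete remission is the same state for 8 weeks. Sixteen weeks implies eight, so sustained remission is the subset and 4.7.3.4 has it backwards.

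**The case against.** The strongest defence is that little is lost.

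- A patient on the exact taper who is clear by the Week 8 visit is counted.
- A patient first clear at Week 12 need not vanish. Partial remission on minimal therapy in 4.7.3.6 asks only for no rise in PDAI over 8 weeks at above 0 to 10 mg, and the 56-day band can satisfy that. The effect is then a drop of one category in a descriptive table.
- Protocol 6.9 leaves the derivation of exploratory endpoints to the SAP.
- No hypothesis test, type I error or power depends on this endpoint.

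All of this stands as a limit on importance. It does not remove the mismatch: a patient with 85 lesion-free days meets the protocol's complete remission and would be shown, at best, as a partial responder.

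A reader might infer three stronger things that the documents do not support.

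- **That ideal responders are missed.** The table shows otherwise for patients clear by Week 8, although with no slack: counting end minus start gives 55 days, and reading the responder rule as still being in the band at Week 24 would also drop them. The SAP states neither rule.
- **That off-therapy remission by Week 24 is impossible.** That holds only for the guideline taper and a Day 168 cut-off. Table 1 gives recommended doses and allows 0 mg sooner; reaching it by Day 113 gives 168 − 113 + 1 = 56 days. SAP 4.6 sets no cut-off for derived remission endpoints. If its midpoint rule for visit data were applied, Week 24 would run to (168 + 224) / 2 = Day 196, with 70 or 63 days at 0 mg.
- **That Week 24 remission will be materially undercounted.** The documents give no distribution of time to clearance or of actual tapers, so no size can be calculated.

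**Conclusion.** The point holds as a definition fault of unknown numerical size. SAP 4.7.3.5 does not analyse the endpoint in protocol 3.4.3 and SAP 2.2.4, its lead sentence conflicts with its own second category, and its count can only equal or fall below the protocol's.

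On the guideline taper, with a Day 168 cut-off and inclusive days, four first-clear visits (Weeks 4, 8, 12 and 16) meet the protocol definition by Week 24. The SAP counts the first two and misses the last two: Week 12 firmly, Week 16 by a margin of one day. Lesion-free time above 10 mg/day is lost in every case.

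For patients who stay clear at 0 mg the shortfall is confined to Week 24, because they complete the off-therapy run by Week 26 or 27 and are counted by Week 52. The primary analysis is unaffected.

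**What to change.** - Make the protocol definition (PDAI activity 0 for at least 8 consecutive weeks, any dose) the main complete remission row at Weeks 24 and 52, and delete the 0 mg/day condition from the lead sentence of 4.7.3.5.
- For the breakdown by dose, let the 8-week run accumulate over 0 to 10 mg/day inclusive and show off-therapy within it. Alternatively, classify by dose at the end of the run, which keeps the categories in 4.7.3.4 mutually exclusive.
- Use the same inclusive range for partial remission in 4.7.3.6, to match the protocol's definition of minimal therapy.
- State the day on which Week 24 ends for derived remission endpoints, the day-count rule for 8 weeks, and whether a response must still be present at the visit.
- Correct 4.7.3.4 to say that sustained complete remission is a subset of complete remission off-therapy.

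The cost is SAP wording and derivation code, with no new data. Exploratory tables need new labels. If off-therapy is shown within the pooled band, the mutual-exclusivity rule in 4.7.3.4 needs a small rewrite.

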4.7.3.6 Partial Remission

PR is defined as having transient lesions that heal within a week (as determined by no increase in PDAI total activity score between visits) for a minimum of 8 consecutive weeks. Two categories of PR will be evaluated: off-therapy and on minimal therapy. A patient will be considered a partial responder if the following criteria are achieved and maintained for a minimum of 8 consecutive weeks:

- PR off-therapy: No increase in PDAI total activity score and prednisone=0 mg/day
- PR on minimal therapy: No increase in PDAI total activity score and $0 < \text{prednisone} \leq 10$ mg/day

The number of patients achieving PR by Week 24 and Week 52 will be summarized descriptively.

All data handling methods will follow those used for the derivation and classification of sustained complete remission.

4.7.3.7 Pemphigus Disease Area Index

The absolute value and change from baseline in PDAI score will be summarized by visit for each treatment arm. Plots of mean total PDAI score over time will be produced.

The main method for dealing with missing PDAI data will be via imputation. Details of PDAI imputation methods are described in Section 4.7.1. Patients who receive rescue therapy will be analyzed up to the point of rescue; no imputation will be carried out for post-rescue data.

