4.7.1.2 Pemphigus Disease Area Index

The PDAI is a scoring system ranging from 0 to 263 and assesses the number and sizes of lesions across cutaneous and mucosal areas of the body, where higher PDAI scores indicate greater disease activity (Appendix 5). The total PDAI score is made up of two components: total activity score (0–250) and total damage score (0–13). The total

Rituximab—F. Hoffmann-La Roche Ltd
17/Statistical Analysis Plan WA29330

damage score measures the extent of post inflammatory hyperpigmentation or erythema from resolving lesions. The trial objective seeks to achieve the absence of new or established lesions (i.e., total activity score=0), with lesser importance being placed on post-inflammatory hyperpigmentation left by lesions that have resolved. For this reason, only the PDAI total activity score will be used for the assessment of sustained complete remission, and will be denoted by PDAI^a throughout this SAP.

For calculating the duration, a patient with a PDAI^a=0 at a visit who fails the criteria at the next visit will be assumed to fail at the date of the visit where PDAI^a=0 was not met. That is, the patient is assumed to maintain the response during the whole interval between the two visits, as any clinically relevant increases in disease activity is expected to be captured by an increase in oral corticosteroids.

Missing Data

Missing PDAI^a scores at a visit will be imputed using the score from the previous or next visit, whichever is higher. If the PDAI^a score is missing at two or more consecutive visits then no imputation will be made, and it will be assumed that PDAI^a>0 for those visits. This imputation will apply for missing overall total scores, and missing anatomical location scores.

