3.7.1.2 Pemphigus Disease Area Index

The absolute value of Pemphigus Disease Area Index (PDAI) activity score will be summarized by visit for each treatment arm.

The main method for handling missing PDAI data will be via imputation. Details of PDAI imputation methods are described in the primary SAP, Section 4.7.1.2.

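### By-visit PDAI means fill an isolated missing score with the higher neighbouring score, a rule written for remission status; when visits are missing at random this tends to overstate activity, mainly at Week 4

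*SAP*

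**What the plan says.** SAP 4.7.3.7 summarises PDAI and its change from baseline by visit and arm, and plots means over time. On missing data it states: "The main method for dealing with missing PDAI data will be via imputation", and refers to Section 4.7.1 for the method. It rules out imputation after rescue.

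The method is in SAP 4.7.1.2, within the description of the components of sustained complete remission:

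- Isolated gap: "Missing PDAI^a scores at a visit will be imputed using the score from the previous or next visit, whichever is higher".
- Longer gap: "If the PDAI^a score is missing at two or more consecutive visits then no imputation will be made"; instead "it will be assumed that PDAI^a>0 for those visits".
- Scope: "This imputation will apply for missing overall total scores, and missing anatomical location scores".

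The safety follow-up SAP, 3.7.1.2, repeats the approach ("The main method for handling missing PDAI data will be via imputation") and cites SAP 4.7.1.2 directly.

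DLQI is treated differently. SAP 4.7.2.5 uses a likelihood-based repeated-measures model and summarises observed data at each visit.

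**The concern.** The rule was built for a yes/no question: is PDAI activity zero throughout the required period? Taking the higher neighbour makes it harder to count a patient as in remission, which is a defensible choice there. A mean asks a different question, and a maximum of two neighbours is one-sided for it. While scores are falling, the gap takes the earlier, higher value. When a patient in remission relapses at the next visit, the relapse is carried back across the gap.

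Week 4 is the most exposed visit. Protocol Appendix 1 schedules no PDAI at Week 2, so the score before Week 4 is Day 1. An isolated missing Week 4 score therefore takes at least the Day 1 value. For an improving patient whose baseline is the Day 1 score, the recorded change is exactly zero.

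The rule also leaves the tables underspecified. An assumption that activity is above zero settles remission status but supplies no number for a mean. Nothing is said about a gap with no later visit.

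Comparing the arms on change in PDAI activity is an exploratory objective (Protocol 2.3). The SAP names no observed-data or model-based version of this summary.

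**Working it through.** **Plan figure.** The documents state no expected PDAI mean and no missing-visit rate, so there is no plan figure to reproduce. From the documents come the PDAI visits (Day 1, Weeks 4, 8, 12, 16, 20, 24, 32, 40, 48 and 52; Protocol Appendix 1), the entry floor of 15 points (Protocol 4.1.1) and the rule itself. Everything else below is assumed.

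**Formula.** Bias in a visit mean = share of contributing patients whose score is filled × average of (higher neighbour − true score).

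**Hand check at Week 4.** Suppose each visit is missing independently with probability q, Day 1 is always present, and longer gaps stay missing. The filled share is q(1−q)/(1−q²) = q/(1+q), which is 0.048 at q = 5% and 0.091 at q = 10%. Take a Day 1 score of 25.

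- Activity halving every 4 weeks: true Week 4 score 12.5, filled value 25, excess 12.5. Bias 0.048 × 12.5 = 0.60 and 0.091 × 12.5 = 1.14.
- Halving every 8 weeks: true score 25 × 0.5^(4/8) = 17.7, excess 7.3. Bias 0.048 × 7.3 = 0.35 and 0.091 × 7.3 = 0.66.

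**Simulation.** This adds variation between patients, visit-to-visit noise and flares. Assumptions: baseline about 25 points with a floor of 15; typical half-life 4 weeks with a 5% flare probability per visit, or 8 weeks with 5% or 15%; visits missing at random. Runs of two or more missing visits were left missing, and an isolated missing Week 52 took the previous score. Bias in points, as the range over the three courses:

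| Visit | 5% missing | 10% missing | 20% missing |
|---|---|---|---|
| Week 4 | 0.5–0.7 | 0.9–1.4 | 1.7–2.5 |
| Week 12 | 0.15–0.21 | 0.28–0.39 | 0.48–0.65 |
| Week 24 | 0.05–0.10 | 0.08–0.19 | 0.14–0.29 |
| Week 48 | 0.03–0.08 | 0.04–0.15 | 0.07–0.23 |
| Average of all visits | 0.15–0.17 | 0.28–0.31 | 0.48–0.53 |

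A filled score exceeded the true score by 3.6 to 4.2 points on average. Observed-data means had bias of about 0.00. Runs of two or more missing visits made up 0.4%, 1.7% and 6.6% of post-baseline visits at the three rates. Follow-up visits, which are 12 weeks apart, were not simulated.

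**Between arms.** With the same disease course in both arms, and 10% missing in one against 5% in the other, the Week 4 means would differ by 1.40 − 0.73 = 0.67 (half-life 4 weeks) or 0.94 − 0.48 = 0.46 (half-life 8 weeks, 5% flares). With different courses the ordering can reverse: at Week 48 the slower, more variable course with 5% missing had bias +0.08, and the faster, stable course with 10% missing had +0.04.

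**If flare visits are the ones missed** (half-life 8 weeks, 10% flares, 8% of other visits missing; average over visits):

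| Flare visits missed, relative to others | Higher-neighbour rule | Observed data |
|---|---|---|
| 1 × | +0.24 | 0.00 |
| 3 × | +0.16 | −0.13 |
| 6 × | about 0.00 | −0.33 |
| 10 × | −0.23 | −0.62 |

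**The case against.** The strongest case for the plan is that missing visits may not be random. If patients skip visits because they are flaring, observed means are too low, and a rule that leans upward compensates. The last table shows this, and the point stands. It is a reason to show both versions, not to rely on the imputed one alone, because the documents do not say which mechanism is expected.

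Visit windows also help. Under SAP 4.6 they run to the midpoints between scheduled visits and can take in unscheduled visits, so Week 4 covers roughly Day 2 to Day 42. A missing Week 4 score means no PDAI in that whole span. This lowers the missing rate; it does not change what the rule does once a score is missing.

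It is also fair to say that making no imputation most naturally means leaving the value missing in a mean. That is probably the intent, and one sentence would settle it.

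A reader might infer more than the text supports:

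- That every missing score is filled upward. Only isolated gaps are, and nothing after rescue is.
- That the rule is worst-case. A flare at the missed visit could score above both neighbours, and a patient in stable remission is correctly given zero.
- That the arm with more missing visits must look worse. This needs more isolated gaps and a similar disease course, and no missing-visit rates by arm are given.

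**Conclusion.** The point holds as a minor one. A rule suited to remission status is carried into by-visit means and changes. With visits missing at random it tends to push them upward: by about 0.5 to 0.7 points at Week 4 with 5% missing and 0.9 to 1.4 with 10%, and by about 0.03 to 0.19 at Weeks 24 and 48 over the same rates. These sizes depend on the assumed baseline, rate of improvement, flare frequency and missing rates. The direction can reverse if flare visits are strongly over-represented among the missing. Any difference between arms depends on both isolated missingness and disease course, and cannot be predicted from the documents.

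It would be wrong to conclude that the trial's confirmatory results are at risk. PDAI change is exploratory and summarised descriptively (SAP 2.2.4 and 4.7.3). No by-visit PDAI mean enters the primary test or the five ranked secondary tests in SAP 4.7.

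**What to change.** In SAP 4.7.3.7 and safety follow-up SAP 3.7.1.2:

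1. Make observed PDAI scores, with n at each visit and arm, the main summary. A repeated-measures model of the kind planned for DLQI may be added if an estimate is wanted.
2. Keep the higher-neighbour rule for remission status. Show it for means only as a sensitivity summary, which also covers the possibility that flare visits are selectively missed.
3. State that runs of two or more missing visits, and gaps with no later visit, stay missing in the means.
4. State how the total is formed when a single anatomical location is blank.

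The cost is a few sentences of SAP text, a slightly smaller n at visits with missing scores, and one extra summary. Data collection does not change.
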